Study Protocol

Official Title: Modulating Default Mode Function: A Transcranial Direct Current Stimulation (TDCS) Pilot Study

ClinicalTrials.gov ID (NCT number): NCT04598152

Protocol Date: 11/24/2020

Scientific Background

Several theories about depression and anxiety suggest that a broad dimension of negative affectivity is shared by the disorders.^{1,3,10,11,15} This dimension represents the tendency to experience negative emotions and to cope inadequately with emotional distress.¹⁶ Recent work in our laboratory has begun to identify and describe one specific component of the broad dimension of negative affectivity, Excessive Self-Consciousness (ESC), that holds promise as a specific phenotype underlying depression and anxiety in adults. This dimension reflects the tendency to feel shame, embarrassment, humiliation, and inadequacy around others.

Preliminary work suggests that it is uniquely associated with impairments in interpersonal functioning over and above psychiatric symptoms, and it is associated with a specific pattern of disruption in the functioning of neural systems during emotional regulation. Specifically, among adults with depression, we have observed that higher levels of ESC are associated with: 1) decreased top-down control from the dorso- and ventrolateral prefrontal cortex (DLPFC, VLPFC; portions of the cognitive control network)^{17,18} during regulation of an initial emotional response in the amygdala; 2) heightened activity during emotion regulation in the precuneus and posterior parietal cortex, regions typically active when thinking about on oneself,¹⁹⁻²¹ and 3) an abnormal pattern of interference by which the abnormally elevated activity in parietal regions alters the patterns of connectivity in the cognitive control network – specifically, decreasing the communication between the DLPFC and the dorsal Anterior Cingulate Cortex (ACC), a region critical for the adaptive regulation of emotional experience.^{17,22} The goal of the proposed project is to determine whether direct, temporary hyperpolarization of portions of the posterior parietal cortex associated with self-referential processing can alter the patterns of abnormal functioning described above and provide a more effective and targeted treatment option for individuals with high levels of ESC, regardless of diagnosis.

Transcranial direct current stimulation (tDCS) provides a safe method for intervening directly on the functioning of brain regions. The technique involves passing a weak current through the brain using a montage of electrodes, pre-selected to target a specific location. Anodal tDCS results in depolarization of cortical pyramidal cells, increasing neuronal excitability and neuronal-neuronal connections. Cathodal stimulation, by contrast, results in hyperpolarization, decreasing neuronal excitability and reducing neuronal-neuronal connections.²³ tDCS has been tested as a potential treatment for both major depressive disorder²⁴⁻²⁷ and anxiety disorders.²⁸ Approximately half of the randomized controlled trials of tDCS have observed significant effects, and half have not.²⁴ When studies are meta-analytically combined, the efficacy of tDCS as a treatment for depression is similar to that observed for standard treatments whereby effect-sizes are small^{24,27} and only 1/3rd of patients respond to the treatment.²⁷ We believe that outcomes from direct interventions like tDCS can be dramatically improved by individualizing them to target the specific pathophysiological mechanisms associated with a particular individual's illness. As such, we hypothesize that by combining our initial results demonstrating that the ESC phenotype is associated with specific patterns of cortical network dysfunction with the targeted intervention capability of tDCS, we will be in a position to develop and test a truly personalized, circuit-based intervention that has the capability of improving treatment outcomes.

Study Objectives

There is growing recognition that strict distinctions between clinical psychiatric disorders such as anxiety and depression, on the one hand, and trait-like dispositions to experience negative emotions, on the other, fail to capture the true nature of psychopathology and are ultimately unhelpful.¹⁻³ We contend that by examining specific dimensional phenotypes that are associated with the experience of negative emotions and that cut across depression and anxiety disorders, we will be better able to identify the neurobiological processes associated with an individual's

distress and to develop better, individually targeted interventions. Recent work in our laboratory has identified one such phenotype, Excessive Self-Consciousness (ESC), that cuts across depression and anxiety disorder presentations, predicts specific impairments in real-world interpersonal functioning, and correlates with a particular pattern of dysfunction in neural systems. In this study, we propose to test whether the ESC phenotype can be used to guide a novel, transcranial direct current stimulation (tDCS) intervention to target specific abnormalities in cortical network functioning.

ESC has long been recognized as one component of the general trait-like disposition to experience negative emotions. It describes the tendency to feel shame, humiliation, and inadequacy around others. In our work with depressed adults, we observed that higher levels of ESC were associated with the following neurofunctional abnormalities during emotion regulation: 1) inefficient functioning of the top-down, cognitive control network necessary to regulate negative emotions; 2) abnormally increased activity in regions of the parietal cortex that are typically active during self-reflection; and 3) a pattern of network interference by which the elevated activity in the parietal regions interfered with communication in the cognitive control network.

In this study, we propose to test whether the ESC dimensional phenotype can be used to guide a novel tDCS intervention to target the network-based abnormalities described above. tDCS involves passing a weak current through the brain. One variant, cathodal tDCS, can be used to temporarily hyperpolarize cortical pyramidal cells, thereby decreasing neuronal connections. tDCS has been explored as a possible treatment for depression, but results to date are mixed. No work has examined whether tDCS can be used in an individually guided manner to target locations in the parietal cortex and alter the patterns of circuitry dysfunction described above. The aims of this study were designed to provide pilot data for a competitive future funding proposal:

1) Determine the impact of acute cathodal tDCS to regions of the left posterior parietal cortex associated with self-reflection on the patterns of abnormal neural activity and connectivity described above. We will compare this to a sham condition whereby no active tDCS will be applied.

2) Determine if the impact of the intervention is greater for those with higher vs. lower levels of ESC, controlling for symptoms of depression and anxiety.

3) Document the feasibility and acceptability of the intervention, and explore whether the tolerability or efficacy of the intervention differs as a function of demographic variables or psychiatric symptoms.

Study Design & Methods

Sample: In order to demonstrate that the patterns of functional neural abnormalities associated with ESC can be specifically altered by cathodal tDCS, we will recruit a sample of 44 adults (18-30 years old, 50% male/female), all of whom will have clinically significant levels of depression (≥ 10 on the Quick Inventory of Depressive Symptoms^{29,30}) or anxiety (≥ 60 on the PROMIS Anxiety Short-form³¹). We are selecting a sample of depressed and anxious adults so that we can confirm that it is the ESC dimensional phenotype, and not psychiatric symptom severity, that is associated with the patterns of cortical functioning abnormalities described above. To ensure an adequate range of ESC scores, the sample will be stratified to require that half (N=22) fall in the upper tertile of ESC scores expected among adults with depression or anxiety² and half (n=22) fall in the bottom tertile.

Procedures: The proposed study will be carried out at the University of Pittsburgh, Magnetic Resonance Research Center (MRRC). Participation will occur over three assessment periods. If participants appear eligible after a telephone screen, they will be scheduled for Visit 1 (which may be virtual or in-person), during which a more thorough set of screening procedures will

determine full eligibility and demographic, symptom, trait, functioning, and life history information will be collected. If participants continue to be eligible following Visit 1, they will be scheduled for two scan visits (Visits 2 and 3) to be held on separate days, approximately one week apart. The following data will be collected:

Initial Eligibility Screening (Visit 1). To determine eligibility, participants will complete the Quick Inventory of Depressive Symptoms (QIDS³⁰) and the Patient Reported Outcomes Measurement Information System Anxiety 7-item short form (PROMIS-A³¹). The QIDS is a 16-item, self-report measure of depression symptoms.^{29,30} Item-response theory analyses suggest cut-offs for moderate depression severity at total scores of 10.^{29,30} The PROMIS-A is an 7-item, self-report tool assessing anxiety. Instrument developers recommend a cutoff for clinical significance at T scores of 60.³² To determine scores on the ESC phenotype, participants will complete the NEO-PI-R,¹⁶ a 240-item inventory that measures the constructs associated with the Five Factor Model of personality, along with the facets of each broad domain. We will use scoring algorithms developed in our laboratory and validated in three separate samples to determine ESC scores.

fMRI Protocol (Visits 2 and 3): At each scanning visit, symptoms (i.e., QIDS, PROMIS-A) will be reassessed. During fMRI at each visit, participants will complete the Cognitive Reappraisal Task. This widely used task examines the functioning of the neural circuitry associated with exerting cognitive control over the response to emotionally salient stimuli.^{34,35} Each trial begins with an instruction cue (2s) to either “attend” or “reappraise” the image that will follow. Next, a negatively or neutrally valenced interpersonally relevant picture is presented (8s) during which participants follow the instructions given for that trial. The task consists of three trial types: attend neutral, attend negative, and reappraise negative. During attend trials, participants view the scene and experience their natural emotional response. During the reappraise trials, participants are asked to reframe the meaning of the scene so as to diminish the negative emotional impact.³⁶ Participants practice the task prior to the scan, and they are provided feedback on their reappraisals of practice items. The stimulus display is followed by an emotional rating probe (4s) and finally a fixation cross (4s) to mark the end of the trial. Twenty trials of each type are presented in a pseudorandom order over two 10 minute, 20 second runs. Two versions of the task have been developed to facilitate repeated testing. These will be counterbalanced across subjects and visits. This task has been used in several studies of healthy adults,³⁷⁻³⁹ and [name] has successfully used the task in a sample of depressed individuals. Prior to fMRI scanning, structural brain data will be collected for all participants. Following the final visit, participants will complete a short, self-report questionnaire regarding their experience of the intervention and will be debriefed by study personnel.

tDCS Protocol (Visits 2 and 3): TDCS will be administered concurrently with the emotion regulation paradigm in the scanner using procedures already in place at the MRRC. TDCS is applied to the scalp, typically providing the equivalent of what a 6V battery would produce (and providing no more than 15V). The TDCS sponge electrodes and connecting wires are non-ferromagnetic and thus can be used safely within the MRI facility. These will be connected to the main apparatus situated outside of the facility. Investigators have determined the optimal placement of wires in the scanning environment to reduce occurrence of scanning artifacts. The montage for left posterior parietal cortex stimulation and the sham will be based on our prior work, the published literature²⁶, and neurotargeting software. We will employ left posterior parietal cortex cathodal stimulation and anodal stimulation on the shoulder. Cathodal stimulation of -1mA will be used, as this produces neural inhibition⁴¹, and because higher cathodal stimulation currents can yield paradoxical excitation⁴². Voltage is controlled by the device to maintain a constant electrode -1mA current. Cathodal stimulation will be applied for the duration of the emotion regulation task (approx. 20 minutes), and it will be slowly ramped up to start and ramped down to end. Previous findings indicate that effects of acute TDCS can last about 2 hours after the procedure but not into the next day⁴². Side effects: mild skin sensations under

the electrode (itching, prickling), dizziness, visual flickering; much less frequently, nausea, headache and more serious atopic skin reactions. There is a built-in safety mechanism to prevent shorting and discomfort. Participants indicate, using a squeeze ball, if they feel scalp warmth. Sham stimulation will be slowly ramped up and down to a nominal low level (1ua).

Eligibility Criteria

Inclusion Criteria:

- 1) Between 18-30years old
- 2) Score > 10 on the QIDS or > 60 on the PROMIS-A
- 3) We will use a flexible extreme groups recruitment strategy to ensure an adequate distribution of ESC scores. We will ensure that at least 62% of the sample will be composed of those scoring .5 SD above or below the mean, as measured by the NEO-PI-R. This value corresponds to the expected values assuming a normal distribution of the trait.
- 4) Normal or corrected to normal vision
- 5) Able to provide informed consent in English
- 6) Right-handed (Annett criteria)

Exclusion Criteria:

- 1) Have a history of head trauma with loss of consciousness.
- 2) Have a systemic medical illness that may impact fMRI measures of cerebral blood flow.
- 3) Meet standard exclusion criteria for fMRI scanning (e.g. claustrophobia, cardiac pacemakers, neural pacemakers, surgically implanted metal devices, cochlear implants, metal braces, or other MRI non-safe metal objects in the body).
- 4) Are pregnant (self-report and tested for as part of any scan by the scanning center)
- 5) Not native English speaking or not fluent
- 6) Premorbid NAART IQ estimate<85;
- 7) Visual disturbance (<20/40 Snellen visual acuity) with correction
- 8) Left/mixed handedness (Annett criteria), to ensure a uniform hemispheric dominance for interpretation of neuroimaging data
- 9) Active suicidal ideation in need of immediate treatment
- 10) Scoring below the cutoffs on both the QIDS and the PROMIS-A
- 11) History of alcohol/substance use disorder (including nicotine) and/or illicit substance use (except cannabis) over the last 3 months, determined by the MINI. Lifetime/present cannabis use (non-disordered levels) will be allowed, given its common usage in individuals in this age range.
- 13) Current or past psychotic-spectrum disorder
- 14) History of seizures

Statistical Considerations

A1: Repeated-measures ANOVA models will be used to determine whether acute cathodal tDCS to the left posterior parietal cortex, compared to the sham condition, alters patterns of neural activity in and connectivity with the posterior parietal cortex and corresponding patterns of activity and connectivity within the cognitive control network during emotion regulation. A2: Repeated measures ANCOVA models will determine whether the impact of tDCS is stronger for those with higher ESC scores, controlling for concurrent depression and anxiety symptoms. A3: Feasibility and tolerability of the intervention will be assessed by examining attrition rates between the fMRI/tDCS visits and by examining responses on the self-report questionnaire regarding the acceptability of the intervention. Differences in acceptance, tolerability, and efficacy will be explored as a function of demographic variables and psychiatric symptoms.

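### The plan says it can confirm that ESC, and not symptom severity, is associated with the neural patterns; the planned model can support only ESC over and above measured severity

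*Combined protocol and SAP*

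**What the plan says.** Study Design & Methods, Sample: "we will recruit a sample of 44 adults", all with clinically significant depression or anxiety, and the reason given for that selection is this: "we can confirm that it is the ESC dimensional phenotype, and not psychiatric symptom severity, that is associated with the patterns of cortical functioning abnormalities". The same paragraph spreads ESC by taking half the sample from the upper tertile, while "half (n=22) fall in the bottom tertile".

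Statistical Considerations, A2, is the one named model that contains both ESC and symptoms. It asks whether "the impact of tDCS is stronger for those with higher ESC scores, controlling for concurrent depression and anxiety symptoms". Aim 2 is worded in the same adjusted way. A3 explores efficacy by psychiatric symptoms, with no model or decision rule.

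Entry on severity needs only one scale: "Score > 10 on the QIDS or > 60 on the PROMIS-A" (Inclusion Criterion 2). The matching exclusion is "Scoring below the cutoffs on both the QIDS and the PROMIS-A" (Exclusion Criterion 10). The fMRI Protocol section has both scales repeated at each scan visit.

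The protocol gives no alpha, power, effect size, equivalence margin or rule for interpreting the symptom terms.

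**The concern.** Saying that severity is not associated is a claim of no effect. A significant ESC coefficient, adjusted for symptoms, shows that ESC carries information that measured symptoms do not. It is silent on whether symptoms carry information of their own; both coefficients can be non-zero at once. Read literally, the negative half would need either a bound on the severity effect or a comparison of the two slopes, and neither is planned.

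The sampling adds to the difficulty. Everyone must pass a symptom cut-off, which narrows the spread of severity, while the tertile rule widens the spread of ESC. The selection offered as the reason for being able to rule severity out makes a severity effect harder to see.

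The study is meant to supply pilot data for a funding proposal in which ESC guides the intervention. A conclusion that severity is irrelevant, if drawn from this sample, could carry into the selection rule of the next study without having been tested.

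**Working it through.** **The plan's own figure.** The sample size of 44 (22 and 22) has no stated derivation, so there is nothing to reproduce.

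**Inputs.** n = 44 comes from the Sample paragraph. Three predictors (ESC, QIDS, PROMIS-A) follow from A2, so each partial correlation is adjusted for two others. Two-sided 0.05 is my assumption.

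**Step 1: what a null severity result would leave open.** On the Fisher z scale, SE = 1/√(n - 3 - 2) = 1/√39 = 0.160. With an observed partial r of 0, the 95% limits are ±tanh(1.96 × 0.160) = ±tanh(0.314) = ±0.30.

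**Step 2: power for the severity term.** Power ≈ Φ(atanh(r) × √39 - 1.96).
- r = 0.2: 0.203 × 6.245 = 1.266; power about 25%.
- r = 0.3: 0.310 × 6.245 = 1.933; power 49% (53% by non-central t).
- r = 0.4: 0.424 × 6.245 = 2.646; power 75% (81% by non-central t).
- r = 0.5: power 93%.

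If attrition left 36 analysed (assumed), power would be 41% at 0.3 and 66% at 0.4. A joint 2-df test of the two scales with 44 people has 41% power when they explain 9% of the residual variance, and 69% at 16%.

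**Step 3: loss of range from the entry cut-offs.** This rests on assumptions. If selection keeps a fraction u of the source-population SD of severity, a source correlation r becomes r·u/√(1 - r² + r²u²).
- Suppose the cut-off acts directly on the severity score analysed. Over assumed source populations, with the two scales correlated 0.5 to 0.7, the SD of combined severity falls to 57-77% of its source value (each single scale keeps 69-89%). A source r of 0.3 becomes 0.18-0.24, with power 20-32%; a source r of 0.4 becomes 0.24-0.32, with power 34-54%.
- Suppose instead that severity is remeasured at the scan visits and correlates 0.7 with its screening value (assumed). The combined SD is then about 0.82. For r = 0.3: 0.246/√(0.91 + 0.0605) = 0.25, power about 36%. For r = 0.4: 0.328/√(0.84 + 0.1076) = 0.34, power about 59%.

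**Step 4: simulation of the full model.** Assumptions: 44 people; ESC from outer tertiles of the eligible; ESC correlated 0.4 with each scale and the scales 0.6 with each other; entry if either scale is more than 0.5 or 1.0 SD above the source mean; ESC and combined severity with equal slopes per source SD; outcome variance 1 in the source. The figures are how often the 2-df symptom test misses the severity effect.

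| True slope of each | Cut-off acts on the analysed score | Remeasured, screening-to-scan r 0.7 |
|---|---|---|
| 0.3 | 80-83% | 66-70% |
| 0.4 | 57-64% | 32-36% |

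The miss rate therefore depends heavily on the effect size and on which symptom score is analysed. Steps 1 and 2 do not depend on the source population.

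**The case against.** **The sentence is rationale, not an aim or a reporting rule.** This is true, and Aim 2 and A2 already use adjusted wording. But the sentence states what the design can confirm, and the design cannot confirm it. That Aim 2 is worded correctly makes the repair easy; it does not make the Sample paragraph right.

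**It may only mean that the ESC association is not explained by severity.** On that reading, enrolling only symptomatic adults controls severity partly by restriction, the narrowed range is intended, and the adjusted ESC term carries the claim. This is a fair reading and may be what was meant. If so, the rewording below says it directly.

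**A reader might infer that a real severity effect would usually be missed.** The documents do not support that without an effect size. An in-sample partial r of 0.4 is detected about 75% of the time or better. Truncation is also only partial: one scale above its cut-off is enough, there is no upper limit, and A2 uses concurrent symptoms, which I take to be the scan-visit scores.

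**A reader might infer that severity would be reported as absent.** No text says that a null symptom term will be reported that way, and A3 does look at symptoms, though only as exploration. Nor does the plan say that ESC drives the patterns; it speaks of association.

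**A reader might quote how often a trial would find ESC significant and severity not.** With equal slopes per source SD, the tertile rule and full truncation, that happens in 53-55% of simulated trials at a slope of 0.3, against 8-10% for the reverse. But this contrast depends on the yardstick. With equal slopes per SD among eligible adults, and the looser ESC rule in Inclusion Criterion 3 ("We will ensure that at least 62% of the sample will be composed of those scoring .5 SD above or below the mean") treated as no enrichment, the two outcomes are about equally frequent: 29% against 27-29%, with severity as a single composite. The documents do not settle which yardstick applies, so neither pair of figures should carry the point.

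**Conclusion.** The concern holds in a limited form. The Sample paragraph claims a capability that the planned analysis lacks: A2 can support ESC over and above measured severity, but not the absence of a severity association, and no margin or direct comparison is planned. With 44 people, a null severity estimate is compatible with partial correlations of about -0.30 to +0.30, and power at 0.3 is about 50%. These two figures assume three predictors, two-sided 0.05 and no attrition. The entry cut-offs lower power further, by an amount the documents do not fix.

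Because this is a pilot and the operative aim is already worded as an adjusted effect, the remedy is wording, reporting and one contrast. It does not call the design into question.

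**What to change.** 1. In the Sample paragraph, replace the claim with: that ESC is associated with these patterns over and above psychiatric symptom severity.
2. In A2, report the symptom effects with 95% confidence intervals beside the matching ESC effect, and state that a non-significant symptom term is not to be read as no association.
3. Allow a statement that ESC matters rather than, or more than, severity only if a direct test of the difference between the ESC and severity slopes, in the same model, supports it. Fix in advance the scale on which the two slopes are compared, since the sample SDs are shaped by the recruitment rules.

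The cost is a more modest claim and one extra contrast from a model already planned; no new data are needed. An equivalence margin should not be required. With two one-sided 5% tests, a true r of 0 and 80% power, it would take about 95 people for a margin of |r| = 0.3 and 214 for 0.2 (both margins assumed); 44 people give 23% power at a margin of 0.3.

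### The counterbalancing rule for the two task versions does not guarantee balance between active and sham, and the order of active and sham is not stated

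*Combined protocol and SAP*

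**What the plan says.** Under Study Design & Methods, the plan sets the sample size ("we will recruit a sample of 44 adults") and the visit schedule: "they will be scheduled for two scan visits (Visits 2 and 3) to be held on separate days, approximately one week apart". The fMRI Protocol section explains why there are two task versions ("Two versions of the task have been developed to facilitate repeated testing") and gives the only rule for using them: "These will be counterbalanced across subjects and visits". Stimulation condition is not named in that rule.

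The tDCS Protocol section says that "TDCS will be administered concurrently with the emotion regulation paradigm in the scanner", so each scan carries one task version and one stimulation condition. The comparator is set in Study Objectives: "We will compare this to a sham condition whereby no active tDCS will be applied". No section says how active and sham are ordered over the two scan visits.

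Statistical Considerations gives the A1 analysis: "Repeated-measures ANOVA models will be used to determine whether acute cathodal tDCS to the left posterior parietal cortex, compared to the sham condition". No term for task version, visit or sequence is named for A1 or A2.

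**The concern.** A1 rests on the difference between each participant's active scan and sham scan. The two scans also differ in the picture set. If one set is more intense or harder to reappraise, that difference enters the active-minus-sham contrast wherever version and condition are unevenly paired. The pairing that has to be balanced is therefore version with condition, and this is the one that the rule leaves out.

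What is at stake is whether a picture-set difference could be read as a tDCS effect on activity or connectivity, in a pilot whose results are meant to support a later funding proposal. If version and condition were fully aliased, no analysis could separate them afterwards. The safeguard has to be in the allocation, before scanning starts.

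**Working it through.** The plan states no figure on this point, so there is none to reproduce. The check asks what the written rule permits.

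**Inputs.** From the documents: 44 participants, two scan visits, two task versions (called A and B here), and one version and one condition per scan. Assumptions: each participant has one active and one sham scan and sees both versions; counterbalanced over visits means that 22 participants have version A at each visit. The number who are active-first, k, is not given and is varied.

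**What the rule permits.** Let n1 be the number who are active-first and A-first. Then 22 − n1 are sham-first and A-first, and (44 − k) − (22 − n1) = 22 − k + n1 are sham-first and B-first. Version A falls in an active scan for the first and third of these groups, so

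m = n1 + (22 − k + n1) = 2·n1 + 22 − k.

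| Active-first, k | Possible n1 | Active scans with version A, m |
|---|---|---|
| 44 | 22 | exactly 22 |
| 33 | 11 to 22 | 11 to 33 |
| 30 | 8 to 22 | 8 to 36 |
| 22 | 0 to 22 | 0 to 44 |
| 11 | 0 to 11 | 11 to 33 |
| 0 | 0 | exactly 22 |

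**The extreme case (k = 22, n1 = 22).** Twenty-two participants have active with A and then sham with B; the other 22 have sham with B and then active with A. Each visit has 22 A and 22 B, everyone sees both versions, and stimulation order is 22/22. Yet A is used in 44 of 44 active scans and 0 of 44 sham scans. A model with 44 subject effects plus visit, condition and version has 47 columns but rank 46, so even adding version to the model cannot separate it from stimulation.

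**Effect on A1.** Write each participant's active-minus-sham difference as d = τ + s·δ + error. Here τ is the tDCS effect, δ is the A-minus-B difference, and s is +1 if the active scan used A and −1 if it used B. The mean of d is then shifted by δ × (2m/44 − 1):

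- m = 44: 1.00 × δ
- m = 33: (66/44 − 1) = 0.50 × δ
- m = 28 or 16: ±12/44 = ±0.27 × δ
- m = 22: 0

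**Independent assignment.** If version order and stimulation order are each split 22/22 and assigned independently, n1 is hypergeometric (44, 22, 22) and m = 2·n1. Its mean is 22, its SD is 3.4 and its central 95% range is 16 to 28. The shift then has mean zero and SD 2 × 3.4/44 = 0.15 × δ. This is sampling noise: s·δ varies between participants and is part of the within-subject residual. The chance of complete aliasing in either direction is 2/C(44,22), about 1 in 10^12.

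**Effect on A2.** A2 asks whether d varies with ESC. If δ is the same for everyone, full aliasing shifts every d by the same amount and cancels from the ESC interaction. Bias there needs both a link between version and condition and a version effect that varies with ESC. Under independent assignment, the version difference adds noise to A2 as it does to A1.

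**Crossed sequences.** With 11 participants in each of four sequences, A is used in 22 of 44 active and 22 of 44 sham scans. The version-condition correlation is 0 and the rank is 47 of 47.

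**The case against.** The plan does not link a version to a condition; it is silent. In a two-scan comparison, the sentence may be shorthand for ordinary crossing, and having two versions for repeated testing suggests that they were meant to be interchangeable. The extreme case needs exactly half the sample active-first and a procedure that ties version to condition; chance would not produce it. If everyone had the same stimulation order, the rule would itself force 22 of 44 active scans onto version A. This is a pilot, and the size of δ is unknown.

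Most of this stands. A reader might infer that the plan confounds the tDCS effect with the picture set, or that A1 carries a bias equal to the whole version difference. The documents do not support that: they contain no rule that pairs version with condition. A reader might also treat the range of 16 to 28 as bias, or take A2 to be as exposed as A1. The working shows that neither follows.

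Two things remain. The sentence does not imply the balance that A1 needs unless everyone has the same order, and in that case stimulation is fully aliased with visit. Intended interchangeability is also not shown: the documents give no evidence that the versions are equivalent, and the decision to counterbalance them treats version as worth controlling.

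**Conclusion.** The point holds as an omission. The rule does not guarantee that task version is balanced across active and sham, and the missing stimulation order means that a reader cannot tell how far it falls short.

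The possible shift in A1 runs from zero to the full version difference. The upper end arises only with half the sample active-first and version tied to condition by procedure. Under independent assignment, the expected shift is zero and the cost is precision, with an SD of about 0.15 of the version difference. A2 also loses precision in that case; it is biased only under a version-condition link combined with a version effect that varies with ESC.

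These results assume one active and one sham scan each, a 22/22 version split at each visit, all 44 participants completing both scans, and, for A2, a pairing rule that does not itself differ by ESC. The version difference is not given, so no absolute size can be attached. The point should be settled before enrolment because full aliasing could not be repaired in the analysis.

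**What to change.** State the order of active and sham over Visits 2 and 3, and replace the version rule with one that crosses the two orders. Allocate participants to four sequences (version A or B first, by active or sham first), about 11 per sequence (4 × 11 = 44). Balance the sequences as nearly as possible over higher and lower ESC. The plan describes ESC sampling in two ways: two halves of 22 under Study Design & Methods, and a flexible extreme-groups rule with at least 62% beyond 0.5 SD under Eligibility Criteria. The balancing should use whichever grouping is finally adopted.

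Add task version and visit as within-subject terms in the A1 and A2 models. Crossing alone centres the A1 estimate, but the version difference would still inflate the residual. The version term removes it, and also handles imbalance left by dropout.

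The cost is a four-row allocation list and one or two degrees of freedom. With 88 scans, the A1 residual goes from 88 − 45 = 43 to 88 − 47 = 41. No participants, visits or procedures are added. If the team already crosses version with condition, recording it is enough for the version rule; the stimulation order and the model terms still need to be stated.
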